Clinical Pathways for Acute Coronary Syndromes in China – Phase 3

*Quality Improvement Initiative to Reduce Cardiovascular Events among
Patients with Acute Coronary Syndromes in Resource-Constrained
Hospitals in China: A Stepped-Wedge Cluster Randomized Trial*

Statistical Analysis Plan

Version 2.2 June 24, 2016

by [name] & [name]

STATISTICAL ANALYSIS PLAN APPROVAL SHEET

Study: CPACS-3

Version: 2.2 (final)

Version date: 24 June 2016

The undersigned have reviewed this plan and find it to be consistent with the requirements of the protocol as it applies to their respective areas. The principal author also finds this plan to be in compliance with ICH-E9 as well as The George Institute's SOP ST-SOP-04.

Signature:_____ **Date**_____

[name], CPACS-3 Statistician

Signature:_____ **Date**_____

[name], CPACS-3 Research Fellow

Signature:_____ **Date**_____

[name], CPACS-3 Principal investigator

Signature:_____ **Date**_____

[name], TGI Chief Scientist

1 Study aims:

The primary aim of CPACS-3 study is to test whether the routine use of a multi-faceted quality of care improvement initiative will lead to a measurable reduction in the number of in-hospital major adverse cardiovascular events (MACE, including total death, non-fatal myocardial infarction and stroke) in patients with ACS presenting to resource-constrained hospitals in China, which was defined as the level two hospitals without PCI facilities and it requires more than 90 min. to transfer patients to the nearest medical centers from these hospitals.

The secondary aims include:

- a) To determine whether the routine use of the initiative will improve quality of care.
- b) To determine the major system-level facilitators and barriers to implementation and uptake of the initiative in resource-constrained settings in China.
- c) To determine the cost-effectiveness of the initiative compared to usual care, from the perspective of the health care provider.

This Statistical Analysis Plan (SAP) will not cover the secondary aims b) and c), since aim b) requires a qualitative study and the way aim c) will be addressed depends upon the results of the primary study, and thus its SAP will be developed separately later. This SAP will be finalized and approved before any analyses with unblinded data.

2 Study Design

CPACS-3 study is a stepped-wedge cluster-randomized trial conducted in 104 resource-constrained hospitals from 15 provinces in China. Patients with acute coronary syndromes (ACS) will be recruited consecutively, with an anticipated total of 25,000 patients recruited within 30 months. All eligible hospitals will be randomised (stratified by province) to 4 wedges. Each wedge contains 26 hospitals. During the first 6 months data will be collected from all hospital participants without any intervention being implemented. Afterwards, the intervention will be implemented sequentially, starting with the first group of 26 hospitals (wedge 1). The second group of hospitals (wedge 2) will start the intervention 12 months later and wedges 3 and 4 will start the intervention at 18 and 24 months later respectively: see Figure 1. By 30 months, all hospitals would have had the intervention implemented for at least 6 months and final data will be collected at this time.

[figure not shown]
The intervention will be applied at the level of the hospital, with outcomes measured at the patient level. The ACS quality of care improvement initiative includes six components:

1. Leadership strengthening and establishment of QCI leaders group
2. Implementation of clinical pathway

3. Hospital performance audit and feedback
4. Training of physicians and nurses
5. Online technical support, and
6. Patient education

All patients discharged alive from hospital will be followed up 6 months later by telephone call.

Figure 1. Visual representation of the stepped wedge design used in CPACS 3

3 Evaluation Outcomes

Primary outcome

The primary outcome is in-hospital major adverse cardiovascular events (MACE), a composite outcome including all-cause mortality, myocardial infarction or re-infarction and stroke. The in-hospital all-cause mortality include patients who died in hospital, those who gave up treatment but died within 1 week after returning home, and those who transferred to upper level hospitals but died within 24 hours.

Secondary outcome

The following secondary endpoints will be considered:

- 1) In-hospital all-cause deaths.
- 2) A patient-level composite score is formed by dividing the total number of pre-defined binary key performance indicators (KPIs) a patient receives (numerator) by the total sum of KPIs a patient is eligible to receive (denominator). However, the length of stay will not be used for the calculation of the composite score.
- 3) Each of the 16 KPIs (15 binary and 1 continuous) of ACS care defined in below table.

- 4) A composite of MACE and re-hospitalization due to cardiovascular disease within 6 months after discharge.

Definitions of 16 KPIs of ACS care		
KPIs	Definition	Denominator
First ECG in time	The patient received the first ECG recorded within 10 minutes after hospital arrival	All patients
Early use of aspirin	The patient received aspirin within 24 hours of arrival at hospital	All patients
Early use of Clopidogrel	The patient received clopidogrel within 24 hours of arrival at hospital	All patients
Early use of statin	The patient received statin within 24 hours of arrival at hospital	All patients
Aspirin prescribed at discharge	The patient prescribed aspirin at hospital discharge	Patients discharged alive
Clopidogrel prescribed at discharge	The patient prescribed clopidogrel at hospital discharge	Patients discharged alive
Beta-blocker prescribed at discharge	The patient prescribed a beta-blocker at hospital discharge	Patients discharged alive
Statin prescribed at discharge	The patient prescribed a statin at hospital discharge	Patients discharged alive
ACEI or ARB prescribed at discharge in the presence of LVSD	The patient with left ventricular systolic dysfunction (LVSD) was prescribed angiotensin- converting–enzyme inhibitors (ACEI) or angiotensin-receptor blockers (ARB) at discharge (LVSD is defined as chart documentation of a left ventricular ejection fraction less than 40% or a narrative description of left ventricular systolic function consistent with moderate or severe systolic dysfunction)	Patients discharged alive and with LVSD less than 40% or heart function grade (KILLIP or NYHA)>=3
STEMI receiving reperfusion (fibrinolysis) therapy	The STEMI patient with ST-segment elevation or LBBB on the ECG and arrive hospital within 12 hours of symptom onset received fibrinolysis within 12 hours of symptom onset.	STEMI patients that arrived hospitals within 12 hours
Acceptable door to needle time	The STEMI patient received fibrinolytic therapy within 30 minutes of arrival at hospital.	STEMI patients that arrived hospitals within 12 hours and received fibrinolytic

		therapy
Diagnosis consistent with ECG and biomarker findings	The patient had its final diagnosis consistent with ECG and biomarker findings	All patients
Length of stay	Number of days of hospitalization	All patients
Three newly added KPIs	Due to the changes in clinical guidelines and clinical practice, it is appropriate to add in the following new indicators.	
Dual antiplatelet therapy	The patient received both aspirin and clopidogrel within 24 hours of arrival at hospital	All patients
Loading dose dual antiplatelet therapy	The patient received both aspirin and clopidogrel with loading dose (i.e. 300 mg or above for each medicine) within 24 hours of arrival at hospital	All patients
Loading dose statin therapy	The patient received statin with loading dose (i.e. 40 mg or above of atorvastatin or equivalent) within 24 hours of arrival at hospital	All patients

*: STEMI: ST-elevated myocardia infraction; NSTEMI: non-ST-elevated myocardia infraction; UA: Unstable angina.

4 Power

Data from our previous CPACS studies estimated the primary outcome to be 8.6% in level two hospitals and the **unadjusted and adjusted intervention effect size was 12% and 59%** [reference 1]. With an improved and better coordinated intervention in CPACS-3, we believe that an expected effect size of 15% to 20% reduction of primary outcome should be reasonable. Assuming an event rate of 8% for the primary outcome and $\alpha = 0.05$, a study with 96 hospitals and 40 patients per cycle from each hospital will provide 98% and 85% power to detect relative risk reduction of 20% and 15%, respectively in the primary outcome. The sample size calculations are based on the assumptions that there is no delay in the effect of the intervention and an **intra-class correlation coefficient of 0.10**. To account for possible drop out of participating hospitals, a total of 104 hospitals will be recruited.

5 Data collection

Baseline characteristics for both hospital and patients were collected. For hospital characteristics, data were collected at the beginning of the study. These included: level of hospital, hospital capacity (number of beds, number of medical personnel, number of outpatient services, number of emergency services), and relevant facilities (including cardiac

catheterization room and hospital information system).

For each patient enrolled into the study, the following information will be collected:

- socio-demographic variables (income, working class status, education);
- symptoms and signs relating to the presenting ACS;
- medical history, electrocardiographic and biomarker findings;
- details of investigations performed;
- details of treatments administered prior to admission, during hospitalization and at death or hospital discharge;
- final diagnosis and discharge status;
- major in-hospital clinical events (stroke, myocardial infarction, re-infarction, major bleeding episodes);
- personal insurance status and cost relating to hospitalization.

One follow-up survey (by clinic visit or telephone) will be conducted by trained hospital staff at 6 months after discharge, to collect information on medications for ACS secondary prevention, MACE and any re-hospitalizations following discharge.

6 Statistical analysis

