6.1 Analysis Principles

The analyses will be conducted by intention-to-treat. All statistical tests will be two-tailed. Treatment effect for the primary and secondary outcomes will be considered significant at $\alpha=0.05$. We will not adjust for **multiplicity**.

We will not impute values unless specified otherwise. We will report the number of observations used in each analysis. Summaries of continuous variables that are normally distributed will be presented as means and SDs and skewed data will be presented as medians and inter-quartile intervals. Categorical variables will be presented as frequencies and percentages.

All analyses on outcomes will be at individual level but account for the clustering of patients in the same hospitals using appropriate statistical models. And except for model 1, all models will be adjusted for time (i.e. "6-month cycle").

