6.4 Main efficacy analyses for the primary outcome

Simple description of primary outcome

The raw percentage of in-hospital MACE will be summarized as n (%) **by wedge and cycle** (**Table 5**) **and by intervention and control** (**Table 5.1**).

Model analysis for primary outcome

In a stepped wedge design more clusters are exposed to the intervention towards the end of the study than in its early stages (one-way). This implies that the effect of the intervention might be confounded with any underlying temporal trend. A result that initially might seem suggestive of an effect of the intervention may therefore transpire to be the result of a positive underlying temporal trend, or vice versa. [reference 2] That means we will **adjust for time in primary analysis**.

The primary analysis will use generalized estimating equations (GEE), an extended form of logistic regression, to compare the odds of in-hospital MACE between intervention and control using all periods' data. Cycle (every 6 months) will be taken as a **fixed effect**, with an **exchangeable correlation structure** to account for clustering (the correlation within hospitals). [reference 3] A robust standard error will be used to guard against misspecification of the correlation structure.

Model 1

Firstly, we will fit a model (**Model 1**) in which we will include the main effect of intervention only,

$$\text{Logit}(p_i) = \beta_0 + \beta_1 \text{Intervention} + e_i$$

Where e_i means the random error in i th patient.

Then, we will examine if there is a time effect in the following two ways:

Model 2 (primary analysis)

Assuming the time effect is non-linear, we will include the main effect of intervention and time (cycle) into Model 2, with cycle treated as a categorical variable (with the first cycle as the reference category) to test if there is a significant intervention effect after adjusting for the time effect.

The log odds of MACE in Model 2 for the i th patient can be written as:

$$\text{Logit}(p_i) = \beta_0 + \beta_1 \text{Intervention} + \beta_2 \text{cycle2} + \beta_3 \text{cycle3} + \beta_4 \text{cycle4} + \beta_5 \text{cycle5} + e_i$$

Model 3

Assuming the time effect is linear, we will include the main effect of intervention and time (cycle) into Model 3, with cycle treated as a continuous variable. The log odds of MACE in Model 3 for i th patient can be written as:

$$\text{Logit}(p_i) = \beta_0 + \beta_1 \text{Intervention} + \beta_2 \text{cycle} + e_i$$

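### The stated 98% and 85% power matches a model without time; under the planned time-adjusted primary analysis (Model 2) it is about 71% and 46%

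*SAP*

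**What the plan says.** Section 4 (Power) bases the calculation on "a study with 96 hospitals and 40 patients per cycle from each hospital", with "Assuming an event rate of 8% for the primary outcome", alpha 0.05 and an "intra-class correlation coefficient of 0.10". It concludes that this "will provide 98% and 85% power to detect relative risk reduction of 20% and 15%, respectively in the primary outcome". The only modelling assumptions it lists are the ICC and an effect without delay. It mentions no time effect and names no formula or software. It describes an expected reduction of 15% to 20% as reasonable.

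Section 6.1 specifies the tests ("All statistical tests will be two-tailed") and says that "except for model 1, all models will be adjusted for time". Section 6.4 warns that a temporal trend can be confounded with the intervention, says the trial will "adjust for time in primary analysis", and labels Model 2 as primary. Model 2 is a logistic GEE with exchangeable correlation within hospital and four indicator terms, for cycles 2 to 5.

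**The concern.** A power statement should describe the analysis that will decide the primary question. In this design every hospital moves from control to intervention and none moves back, so the share of exposed hospitals rises with each cycle. Once cycle effects are estimated, much of the information about the intervention is used up in separating it from time. A calculation that leaves them out can overstate power badly.

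What is at stake is how the result is read. Someone who believes the trial had 85% power for a 15% reduction will take a non-significant primary result as fairly strong evidence against an effect of that size. If the true figure is near one half, that reading is wrong.

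**Working it through.** **Inputs**
- Section 4: I = 96 hospitals, n = 40 per hospital per cycle, control rate 8%, ICC 0.10, reductions of 20% (8.0% to 6.4%, difference 0.016) and 15% (8.0% to 6.8%, difference 0.012).
- Section 6.1: two-sided alpha 0.05.
- Sections 2 and 6.4: 4 wedges (24 hospitals each at I = 96) and T = 5 six-month cycles, the first all control. Starts are taken at months 6, 12, 18 and 24.

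**Variance components.** Total variance is p̄(1 − p̄), with p̄ the mean of the two rates. For a 20% reduction, p̄ = 0.072 and the total is 0.066816.
- Between hospitals: τ² = 0.10 × 0.066816 = 0.0066816
- Within, per hospital-cycle mean: σ² = 0.90 × 0.066816 / 40 = 0.00150336
- σ² + Tτ² = 0.0349114

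**Design constants.** With X = 1 for an exposed hospital-cycle:
- U = ΣX = 24 × (4+3+2+1) = 240
- W = Σ over cycles of (exposed hospitals)² = 24² × (1+4+9+16) = 17,280
- V = Σ over hospitals of (exposed cycles)² = 24 × (16+9+4+1) = 720

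**Step 1: reproduce the stated figures, no cycle effects.** With c = τ²/(σ² + Tτ²) = 0.19139,

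Var = 1 / [ (U − cV)/σ² − U²/(IT(σ² + Tτ²)) ] = 1 / (67,982 − 3,437) = 1.549 × 10⁻⁵, SE = 0.003936.

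- 20%: 0.016/0.003936 = 4.065; Φ(4.065 − 1.960) = **98.2%**
- 15% (p̄ = 0.074, SE = 0.003986): 0.012/0.003986 = 3.010; Φ(1.050) = **85.3%**

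Both stated figures are matched.

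**Step 2: add categorical cycle (Model 2), Hussey-Hughes variance.**

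Var = Iσ²(σ² + Tτ²) / [ (IU − W)σ² + (U² + ITU − TW − IV)τ² ]

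Here IU − W = 23,040 − 17,280 = 5,760, and U² + ITU − TW − IV = 57,600 + 115,200 − 86,400 − 69,120 = 17,280.

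Var = 96 × 0.00150336 × 0.0349114 / (5,760 × 0.00150336 + 17,280 × 0.0066816) = 4.059 × 10⁻⁵, SE = 0.006371.

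- 20%: 0.016/0.006371 = 2.511; Φ(0.551) = **70.9%**
- 15% (SE = 0.006452): 0.012/0.006452 = 1.860; Φ(−0.100) = **46.0%**

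The variance ratio of Step 2 to Step 1 is 4.059/1.549 = 2.62.

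**Step 3: cross-checks of Model 2.**
- Logit-scale GEE information with exchangeable correlation: 70.1% and 45.6%.
- Standard stepped-wedge design effect: 70.9% and 46.0%.
- Simulation with beta-distributed hospital rates, GEE with robust SE, 500 runs per setting: 71.4% and 47.2% (Model 1 in the same simulation: 98.4% and 83.2%).

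**Step 4: can another time-adjusted reading restore 98% and 85%?**

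| Variant | 20% | 15% |
|---|---|---|
| Variance taken at the 8% rate | 67% | 43% |
| p(1 − p) taken as within-hospital variance (8% or mean rate) | 62–66% | 40–42% |
| Linear cycle (Model 3) | 71% | 46% |
| ICC 0 instead of 0.10 | 86% | 61% |
| One-sided alpha 0.05 | 81% | 59% |
| Event rate 8.6% | 74% | 49% |
| Wedge 2 at month 18, wedges 3 and 4 both in the last cycle | 65% | 41% |
| 104 hospitals × 40 | 74% | 49% |
| 25,000 patients in 104 hospitals (25,000/104/5 ≈ 48 per cycle) | 82% | 56% |

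None does. With 96 hospitals, about 100 patients per hospital per cycle would be needed to come near (97.6% and 83.1%).

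**Step 5: detectable reduction at 80% power under Model 2.** Solving 0.08 × r = (1.960 + 0.842) × SE(r) gives r = 22.2% at 96 × 40 and 19.6% with 25,000 patients.

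**The case against.** Four points can be made for the plan.

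- *The cause is inferred.* Section 4 names no method, so the omission of time is deduced from a numerical match. The match also does not pin down the other inputs: without cycle effects, an ICC of 0.01 gives 98.0% and 84.4%. This stands as a limit on what can be said about how the figures arose. It does not rescue them, because under Model 2 the stated inputs cannot give them.
- *96 × 40 is the planning minimum.* The trial anticipates 25,000 patients, not 96 × 40 × 5 = 19,200. Power is then about 82% for 20%, a conventional level, and 56% for 15%. So it is only at the planning size that a true 15% reduction would be missed more often than found. This stands, and both sizes should be reported. But Section 4 makes its claim at 96 × 40, and it presents the 104 hospitals as an allowance for dropout.
- *Misreading is not certain.* Section 6.4 already requires odds ratios with 95% confidence intervals, and nothing in the SAP equates non-significance with no effect. That is true and lowers the risk. The plan would still give readers a power figure that invites the misreading.
- *The validity of the analysis is unaffected.* Model, test and tables do not change. This is correct, and it is why the remedy is limited to wording.

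**Conclusion.** The concern holds. With the SAP's own inputs, power under the declared primary analysis is about 71% and 46%, not 98% and 85%: a shortfall of 27 and 39 percentage points. Other variance conventions lower it to as little as 62% and 40%, so 71% and 46% are at the favourable end. At the anticipated 25,000 patients it is about 82% and 56%.

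The detectable reduction at 80% power (22.2%) lies outside the expected 15% to 20% range at the planning size, and at its upper edge (19.6%) at full enrolment.

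These figures rest on starts at months 6, 12, 18 and 24, equal numbers per hospital and cycle, and one constant within-hospital correlation, as the exchangeable structure implies. If the correlation between cycles were 0.9 of that within a cycle (an assumption; the SAP gives no value), power at 96 × 40 would be about 56% and 34%. The conclusion does not depend on that scenario.

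**What to change.** Restate Section 4 under Model 2:

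- Power of about 71% and 46% for reductions of 20% and 15% at 96 hospitals × 40 per cycle, and about 82% and 56% at 25,000 patients in 104 hospitals. Name the formula and the variance convention, and give the range (62–71% and 40–46% at 96 × 40).
- Detectable reduction at 80% power: about 22% at 96 × 40 and 19.6% at 25,000 patients.
- A statement that 98% and 85% correspond to a calculation without period effects, once the trial statistician has confirmed this from the original calculation.
- A sentence that a non-significant primary result does not by itself exclude a 15% reduction and is to be read from the confidence interval.

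The cost is SAP wording and a less favourable power statement. Enrolment, the primary model and the tables do not change. Model 2 should stay primary: moving to Model 1 to recover the stated power would bring back the confounding by time that Section 6.4 sets out to remove.

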6.1 Analysis Principles

The analyses will be conducted by intention-to-treat. All statistical tests will be two-tailed. Treatment effect for the primary and secondary outcomes will be considered significant at $\alpha=0.05$. We will not adjust for **multiplicity**.

We will not impute values unless specified otherwise. We will report the number of observations used in each analysis. Summaries of continuous variables that are normally distributed will be presented as means and SDs and skewed data will be presented as medians and inter-quartile intervals. Categorical variables will be presented as frequencies and percentages.

All analyses on outcomes will be at individual level but account for the clustering of patients in the same hospitals using appropriate statistical models. And except for model 1, all models will be adjusted for time (i.e. "6-month cycle").

6.2 Eligible sample size for analyses

Our analyses will include only patients with final diagnosis of STEMI, NSTEMI, and UA with non-missing discharge status (primary outcome) who also meet the inclusion and exclusion criteria defined by the study protocol.

The eligible sample size by wedges and by cycles will be presented in **Table 1**

The eligible sample size at each hospital will be presented in **Table 2**.

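### Section 6.2 selects patients on a final diagnosis made after exposure, so the analysed set can shift at each hospital's roll-out, and no planned analysis relaxes that filter

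*SAP*

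**What the plan says.** SAP section 6.2 sets the analysis population: "Our analyses will include only patients with final diagnosis of STEMI, NSTEMI, and UA with non-missing discharge status (primary outcome". It adds a second condition, "who also meet the inclusion and exclusion criteria defined by the study protocol". The word 'also' makes the final-diagnosis rule a further filter rather than a restatement of eligibility. Section 6.1 says "The analyses will be conducted by intention-to-treat".

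Other parts of the SAP bear on the label used as the filter:

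- Section 5 lists final diagnosis together with discharge status among the items collected for each patient.
- The KPI table in section 3 scores a diagnosis indicator, "The patient had its final diagnosis consistent with ECG and biomarker findings", with all patients as its denominator. Section 6.6 includes it in the composite score.
- Secondary aim a in section 1 is "To determine whether the routine use of the initiative will improve quality of care". The components in section 2 include a clinical pathway, staff training and "Hospital performance audit and feedback".
- Section 2 says "Patients with acute coronary syndromes (ACS) will be recruited consecutively".

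Section 6.10 plans two kinds of sensitivity analysis: one leaves out hospitals with poor data quality, the other adjusts for an intervention index. Neither changes the final-diagnosis rule.

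**The concern.** The SAP treats diagnostic labelling as something the initiative may improve, and then uses the label to decide who is analysed. That is selection on a variable measured after exposure. If, after roll-out, a hospital gives an ACS label to more low-risk patients who would previously have left with a non-ACS diagnosis, the observed MACE rate falls with no patient better off. If it stops giving that label to low-risk patients, the rate rises and a real benefit could be hidden.

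Model 2 adjusts for calendar cycle. A labelling shift would begin at each hospital's own crossover, so it follows the intervention indicator rather than the cycle terms.

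The diagnosis KPI has a related defect. An ACS patient wrongly given a non-ACS final diagnosis is removed by section 6.2 and can never be scored as inconsistent, so the indicator cannot see that class of error.

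**Working it through.** The SAP gives no figure for the effect of this restriction, so there is none to reproduce.

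**Inputs.** From SAP section 4: event rate p = 8%; design effects of 15% and 20% relative risk reduction (RRR); 96 hospitals; 40 patients per hospital per cycle; ICC 0.10. From sections 2 and 6.4: four wedges and five cycles. From section 6.1: "All statistical tests will be two-tailed", at 0.05. Assumed, because the SAP gives neither: the added volume a (as a fraction of the existing set) and the event risk q of the added patients.

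**Step 1: which relabelling matters.** Moves among STEMI, NSTEMI and UA leave the set unchanged. Only moves between ACS and non-ACS alter it.

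**Step 2: spurious effect with no true benefit.** Observed rate = (p + a·q)/(1 + a). With f = a/(1 + a), the share of newly counted patients, RRR = f(1 − q/p).

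- a = 10%, q = 2%: (0.08 + 0.10 × 0.02)/1.10 = 0.0745; RRR = 1 − 0.0745/0.08 = 6.8%.
- a = 25%, q = 2%: (0.08 + 0.25 × 0.02)/1.25 = 0.068; RRR = 15%.

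| q (assumed) | RRR at f = 5% | RRR at f = 10% | RRR at f = 20% | f needed to mimic RRR 15% |
|---|---|---|---|---|
| 0% | 5.0% | 10.0% | 20.0% | 15% |
| 2% | 3.75% | 7.5% | 15.0% | 20% |
| 4% | 2.5% | 5.0% | 10.0% | 30% |

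**Step 3: the opposite direction.** If 10% of the set, at 2% risk, is dropped after roll-out, the rate becomes (0.08 − 0.10 × 0.02)/0.90 = 0.0867, a spurious relative increase of 8.3%.

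**Step 4: effect on the test.** Simulation with no true benefit, 1000 trials per setting: beta-binomial hospitals, the section 4 inputs, categorical cycle effects, exchangeable working correlation and robust standard error, on the linear scale, with q = 2%. Two-sided rejection rates:

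- f = 0: 5.3%
- f = 5%: 8.3%
- f = 10%: 15.6%
- f = 20%: 42.2%

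The Monte Carlo standard error near 5% is √(0.05 × 0.95/1000) = 0.7 percentage points.

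**Step 5: whether planned outputs would show it.** Tables 1, 3.1 and 4 describe the retained patients by wedge, cycle or exposure. None counts those removed by the filter or gives the reason.

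**The case against.** The strongest reply has five parts.

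**No shift is shown.** A reader might infer that the set does change at roll-out, or that MACE will fall artificially. The SAP has no data on either, and the direction is open. The KPI concerns agreement with test findings. Nothing says the initiative aims at the ACS/non-ACS boundary, or that this indicator is among those fed back to hospitals. This stands, and the point is limited to what can happen.

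**Intention-to-treat is not breached.** A reader might infer a contradiction with section 6.1. Hospitals are the randomised units, and section 6.2 does not alter any hospital's assigned exposure. At cluster level the principle holds. What is affected is the comparability of the patients counted within hospitals.

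**The aim concerns ACS patients.** Making all enrolled patients the main set would change the target population and score non-ACS patients on ACS treatment indicators. This also stands, so the main set should not be replaced.

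**The protocol is not shown.** If it enrols on final diagnosis, the two sets coincide and the selection sits at enrolment. The word 'also' in section 6.2 points the other way but does not settle it. Recognition of ACS at admission could shift with training too, so the wider set is a check, not an unbiased standard.

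**Part of the check is planned.** Table 1 would show a jump in retained numbers, Table 4 compares case mix by exposure, and covariate-adjusted models might absorb some of the shift. But a jump in retained numbers cannot be told apart from a change in admissions, and the adjusted models are secondary and cannot restore excluded patients.

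**Conclusion.** The concern holds as a possible bias that the plan leaves untested. Membership of the analysis set depends on a label assigned after exposure, and a change across the ACS/non-ACS boundary at crossover would be read as an intervention effect on MACE, death or KPIs.

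The size depends on assumed figures. With added patients at 2% risk forming 5% of the set, the spurious RRR is 3.75%, which matters little. At about 10% of the set it is 7.5%, half of the smaller design effect. At 20% it equals that effect. The documents do not say which of these, if any, is realistic, and removal of low-risk patients would reverse the sign. This does not show that the primary result will be biased, and it does not justify abandoning the ACS population. It justifies a named check before unblinded analysis.

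**What to change.** - Section 6.2: keep the final-diagnosis set as the main ACS analysis.
- Section 6.10: add a named sensitivity analysis of Model 2 for in-hospital MACE and in-hospital death in all enrolled patients who meet the protocol criteria, regardless of final diagnosis.
- Table 1: report, by wedge, cycle and exposure, the numbers excluded for a non-ACS final diagnosis, the numbers excluded for missing discharge status, and the UA share of those retained.
- Section 6.7: compute the diagnosis-consistency KPI also on all enrolled patients.

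The cost is a few lines of SAP text, two further Model 2 runs, one further KPI calculation and extra rows in Table 1. The sensitivity set will be somewhat diluted by non-ACS patients, so a modest attenuation there should not by itself be read as evidence of bias. The proposal assumes that patients with a non-ACS final diagnosis are in the database, as the filter implies. If they are not, report patient volume and UA share by exposure and state the limitation.
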